More recent studies have clarified that the sensitivity of PPI to drug effects in normal humans is moderated by several factors, including the presence of specific genes, and personality dimensions associated with those genes. For example, several groups have reported that PPI and its sensitivity to drug challenge differs significantly between normal men who carry different alleles for the COMT Val158Met polymorphism. In these studies, the Val/Val allele is associated with high COMT activity, rapid DA catabolism, high novelty seeking scores, low basal PPI and PPI-enhancing effects of the COMT inhibitor, tolcapone. In contrast, the Met/Met allele is associated with low COMT activity, low DA catabolism, low novelty seeking scores, high basal PPI, and PPI-reducing effects of tolcapone. We previously reported that rats expressing high levels of COMT within the ventral striatum exhibit PPI-enhancing effects in response to DA agonists, like amphetamine, while rats expressing low levels of COMT in this region exhibit PPI-reducing effects in response to amphetamine. More recently, we confirmed that normal women with high novelty seeking scores (who as a group predominantly express the Val/Val high activity COMT allele) respond to amphetamine with elevations of PPI, while those with low novelty seeking (associated with the Met/Met low activity COMT allele) respond to amphetamine with reduced PPI. We also detected PPI-enhancing effects of the NMDA antagonist and weak DA agonist, memantine, among men exhibiting low baseline PPI and/or high novelty seeking, both of which are associated with the Val/Val COMT genotype. Thus, across species, genetically determined levels of COMT activity appear to moderate the impact of specific drugs on sensorimotor gating. These findings suggest a biological explanation for a genetically based "vulnerability" to the gating-disrupted effects of increased dopamine activity and/or reduced NMDA activity, thought to be core features of brain disorders such as schizophrenia and Tourette Syndrome. We now plan to extend this work to further clarify the role of COMT polymorphisms and other genetic substrates on the sensitivity of PPI to drug effects in humans.

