For example, to assess the effects of memantine on "gating" measures in schizophrenia patients, the primary measure will be evaluated by 2-way repeated-measure ANOVA of PPI with memantine dose and prepulse interval as within-subject factors. The hypothesis that memantine will increase PPI in schizophrenia patients will be confirmed by a significant effect of dose (active > PBO) or significant dose x interval (int) interaction and post-hoc comparisons at one or more prepulse intervals. Existing data (see above) provide a strong *a priori* prediction that the 120 ms prepulse interval will be most sensitive to PPI-enhancing effects of MEM. The effect size (d) for PPI-enhancement by 20 mg memantine in HCS was 0.91; with a similar "d" in patients, 30 patients/dose yields power of 0.92 to detect the predicted memantine effects; with maximum expected attrition (n=24), power is 0.85. Past findings also lead to the prediction that these MEM effects would be most robust in subjects exhibiting the lowest basal PPI levels (d=1.80). Using a median split of mean basal (screening) PPI levels, ANOVA as above will detect a significant interaction of memantine dose x basal PPI level, or dose x basal level x int, and significant post-hoc comparisons at one or more prepulse intervals (again, 120 ms being the strongest *a priori* candidate). Given the published "d" in control subjects, a comparable "d" in the proposed 12-15 "low PPI" patients/dose group would yield power >0.95 to detect the predicted memantine effects.

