Lastly, based on the impact of basal PPI level and personality measures in controls, we hypothesize that a critical moderating factor underlying PPI memantine sensitivity is COMT Val158Met genotype; specifically, we predict that “Val/Val” individuals will be most sensitive to memantine-enhanced PPI. This will be tested in two ways: first, by ANOVA as above, with COMT status as a between-subject factor, and memantine dose and prepulse interval as within-subject factors. Significant genotype x dose or genotype x dose x int interactions, with appropriate post-hoc comparisons, would confirm the hypothesis. Estimating $d=1.53$, based on the mean “d” of two “COMT phenotypes” in controls – low basal PPI ($d=1.80$) and high “novelty seeking” personality ($d=1.27$) - the proposed 11 Val/Val and 7 Met/Met patients/dose group would yield power of 0.90 to detect genotype-sensitive memantine effects. It is possible that various factors (including a skewed distribution of allele frequencies, or substantial genotype effects on basal PPI levels) might preclude detection of a significant 2- or 3-way interaction. A secondary (albeit weaker) test of the hypothesis will utilize separate ANOVAs in Val/Val vs. Met/Met subgroups, with predicted PPI-enhancing effects of memantine in the Val/Val but not Met/Met subgroups. Previous reports also predict a significant main effect of genotype, with PPI levels following the Met/Met>Val/Met>Val/Val gradient. Logistic regressions might be used, with genotype coded to reflect “dose” of the Met allele (Val/Val=0, Val/Met=1, and Met/Met=2), to assess the distribution of the neurophysiological and neurocognitive measures. All analyses will be conducted independently for each dose group. If comparable effects are evident with 10 and 20 mg doses, dose groups may be pooled to increase power for exploratory analyses (e.g. to detect genotype x drug effects).

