Main effects of memantine on WM will be tested by one-way ANOVA with memantine dose as a within-factor. Based on $d=0.73$ for increased WM after 20 mg MEM in controls (see above), the proposed 30 patients/dose group would yield power of 0.79 to detect significant WM-enhancing effects. While preliminary data yield less robust predictions for COMT subgroup sensitivities in memantine effects on WM performance, given the significant correlation of WM and PPI, and known impact of COMT genotype on PPI levels, we predict some differential (Val/Val > Met/Met) memantine sensitivity in this measure. If we estimate effects of COMT status on WM memantine-sensitivity to be comparable to those for PPI (65% increase in effect size), then the estimated d for Val/Val vs. Met/Met sensitivity should be 1.20, and the proposed genotype subgroup sizes would yield power of 0.65 to detect genotype-sensitive memantine effects on WM.

Secondary “biomarkers” are MMN and GBS. For MMN, positive memantine effects will be detected by increased MMN amplitude at electrode Fz. For GBS, positive memantine effects would be detected by increased 40 Hz evoked power at electrode Fz. Unlike those for PPI, predictions of positive memantine effects on MMN and GBS are not based directly on previous findings from our laboratory, using measures identical to those proposed herein. However, based on reports in healthy subjects from other laboratories of memantine effects on MMN ($d=0.87$) and ketamine effects on GBS ($d=0.69$), the proposed 30 patients/dose group would yield power of 0.90 and 0.75, respectively, to detect positive memantine effects on these measures.

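### The working-memory genotype power (0.65) enters memantine's effect in the sensitive subgroup as the Val/Val-minus-Met/Met difference; the PPI figure is built the same way and is 0.84, not 0.90, even in its best case

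*Protocol*

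**What the plan says.** All of this stands in Protocol section 9.j (Statistics, power considerations).

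- **Test.** For PPI, the moderator hypothesis is confirmed by a significant interaction of genotype with memantine dose, with or without prepulse interval. Alpha is 0.05; sidedness is not stated.
- **PPI effect sizes.** "The effect size (d) for PPI-enhancement by 20 mg memantine in HCS was 0.91". The plan then expects that "these MEM effects would be most robust in subjects exhibiting the lowest basal PPI levels (d=1.80"), and applies that 1.80 as the drug effect within the 12-15 low-PPI patients of each dose group. For genotype it takes d = 1.53, "based on the mean “d” of two “COMT phenotypes” in controls": low basal PPI (1.80) and high novelty seeking (1.27). With 11 Val/Val and 7 Met/Met, these "patients/dose group would yield power of 0.90 to detect genotype-sensitive memantine effects".
- **PPI prediction for Met/Met.** As a secondary test, the plan describes separate subgroup ANOVAs and predicts enhancement in Val/Val and none in Met/Met.
- **WM.** The whole-sample d is 0.73. The plan supposes that COMT affects WM sensitivity as it does PPI sensitivity, a 65% increase in effect size; "then the estimated d for Val/Val vs. Met/Met sensitivity should be 1.20", and power is 0.65. It predicts some difference between the genotypes, not an absent response in Met/Met, and calls its preliminary data less robust here than for PPI.

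The SAP describes the PPI and MCCB analyses and does not mention genotype.

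**The concern.** A genotype x drug interaction compares two drug effects: memantine minus placebo in Val/Val, less memantine minus placebo in Met/Met. Power for it needs the size of that difference. The WM figure of 1.20 is the overall drug effect inflated by 65%, so by construction it is the effect expected within the more responsive genotype. The sentence that derives it then names it as the contrast between genotypes. No Met/Met effect is stated or subtracted anywhere in section 9.j.

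If Met/Met patients respond to any positive degree, the true contrast is smaller than 1.20 and the power is lower than stated for the same SD. Genotype moderation is a named part of Aim 3, and the SAP is silent on it, so these two protocol figures are the only stated basis for reading a null interaction. Powers of 0.90 and 0.65 invite more weight on such a null than the design can bear.

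**Working it through.** **Inputs** (Protocol 9.j unless marked): alpha 0.05, taken as two-sided (assumption, as for an ANOVA F test); group sizes 11 and 7; whole-sample d 0.91 (PPI) and 0.73 (WM); subgroup d 1.80 and 1.27 (PPI); WM multiplier 1.65. Met/Met d: not given.

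**Step 1. Where the two d values come from.**
- WM: 0.73 x 1.65 = 1.2045, stated as 1.20.
- PPI: (1.80 + 1.27)/2 = 1.535, stated as 1.53. The ratio 1.53/0.91 = 1.68 is close to the multiplier carried to WM.

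Both are drug effects in a responsive subgroup. The plan's own use of 1.80 for the low-PPI patients alone confirms this for that component.

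**Step 2. Reproduce the stated power.** Two-sample t, df = 11 + 7 - 2 = 16, critical value 2.120, noncentrality = d / sqrt(1/11 + 1/7) = d / 0.4835.
- WM: 1.20/0.4835 = 2.48, power 0.645. This matches 0.65, so the whole 1.20 was entered as the between-genotype difference.
- PPI: 1.53/0.4835 = 3.16, power 0.844. This does not match 0.90; by this test 0.90 needs d of about 1.67.

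Other methods come closer to 0.90 for PPI: a two-sided normal approximation gives 0.886 and a one-sided t gives 0.916. For WM they give 0.699 and 0.767, so neither reproduces both stated figures.

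**Step 3. Power for the contrast that is tested.** Contrast = d(Val/Val) - d(Met/Met). The Met/Met values are assumptions, and d is taken as scaled to the SD of the drug-placebo change.

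| Assumed Met/Met d | WM contrast | WM power | PPI contrast | PPI power |
|---|---|---|---|---|
| 0 | 1.20 | 0.65 | 1.53 | 0.84 |
| 0.2 | 1.00 | 0.49 | 1.33 | 0.73 |
| 0.4 | 0.80 | 0.34 | 1.13 | 0.59 |

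**Step 4. Dependence on the SD behind d.** The plan does not say what SD scales d. Its WM main-effect power (d = 0.73, n = 30, stated 0.79) is matched by an independent two-sample t with 30 per group (0.794); a paired test would give 0.97. So d may be on the raw-score SD. In that case the SD of the change is sqrt(2(1 - r)) times the raw SD, where r is the within-subject correlation, and the contrast in Step 3 is divided by that factor.
- r = 0.5: factor 1, table unchanged.
- r = 0.8 (assumed): factor sqrt(0.4) = 0.632. WM power with Met/Met at 0 is 0.96, and 0.65 is still reached with a Met/Met d of about 0.44.
- r = 0.25 (assumed): factor sqrt(1.5) = 1.225. WM power with Met/Met at 0 is 0.48.

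**The case against.** **PPI.** Computing power under the stated hypothesis is ordinary practice, and for PPI the plan does predict no enhancement in Met/Met. This stands: the PPI construction is a disclosed best case without a sensitivity range, not a contradiction. It does not rescue 0.90, which the t test behind 0.65 misses even in that case.

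**Necessity of a zero response.** A reader might infer that the stated powers hold only if Met/Met patients do not respond at all. The documents do not support that. A negative Met/Met effect would raise power: at -0.3, Step 3's method gives 0.83 for WM and 0.94 for PPI. Section 7 reports PPI-reducing effects in Met/Met or low-novelty-seeking groups, though with tolcapone and amphetamine, not memantine. The unstated SD matters too: on a raw-score SD with a high within-subject correlation, 0.65 could survive a moderate positive Met/Met effect. Neither point turns a subgroup effect into a contrast.

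**A single corrected figure.** One might also back-solve the Met/Met effect from the whole-sample d and the planned genotype split. That would apply the patients' planned split to effect sizes from healthy controls, whose genotype mix is not given, and average standardised effects as if they shared one SD. The result would be assumption, not something the plan implies.

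**Phenotype as proxy for genotype.** Section 7 describes high novelty seekers as a group "who as a group predominantly express the Val/Val high activity COMT allele", which suggests that phenotype-based effects overstate the genotype effect. But that remark concerns women given amphetamine; for memantine in men the section reports only an association. The documents do not let the dilution be sized.

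**Consequence.** The plan already cautions that an interaction may be missed, words the WM estimate conditionally, and admits power of only 0.65. This limits the harm. It does not disclose that 0.65 is itself the no-response case.

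**Conclusion.** The point holds for WM as an error in the stated contrast: 1.20 is a sensitive-subgroup drug effect labelled as a between-genotype difference, and 0.65 follows from entering it whole. That amounts to a null Met/Met response, which goes beyond the partial difference the plan predicts for WM. For PPI it holds in a weaker form: the null response is the plan's own prediction, but no sensitivity is shown, and 0.90 should be about 0.84 under the method that returns 0.65.

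On the change-score SD, moving the Met/Met effect from 0 to 0.4 takes WM power from about 0.65 to 0.34 and PPI power from about 0.84 to 0.59. These sizes rest on a two-sided t test, full 11 and 7 groups, assumed Met/Met effects, and that scaling of d. On a raw-score SD they rise when the within-subject correlation exceeds 0.5 and fall when it is lower.

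What changes is how a non-significant genotype x drug result may be read. It would be wrong to infer that the memantine main-effect powers or the SAP's primary conclusions are affected; neither uses these figures.

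**What to change.** In the two genotype paragraphs of Protocol section 9.j:

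1. Define the genotype d as the Val/Val drug effect minus the Met/Met drug effect.
2. State the assumed Met/Met effect for each outcome, and the SD that scales d (drug-placebo change or raw score; if raw, the assumed within-subject correlation).
3. Restate the PPI best case as about 0.84, or name the method that gives 0.90 and use it for WM as well.
4. Replace each single figure with power over a range of Met/Met effects labelled as assumptions, with zero response shown as one case. The table under the working can serve as a template once the SD is settled.
5. Report the genotype x drug estimate with its 95% CI, so that a null result is read by its precision.

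The cost is a few sentences and figures that look less favourable. No change to design, sample size or the main-effect calculations is needed.

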10. HUMAN SUBJECTS

The subject population will include normal controls and individuals with existing diagnoses of schizophrenia. Men and women will be represented and ethnic representation in the sample groups will be determined by recruitment responses. Exclusion criteria for control subjects are psychiatric disorders in self or first degree relative, organic brain dysfunction, pregnancy or history of substance abuse. Psychiatric subject exclusion criteria are serious medical or neurologic illness, history of seizures, sustained loss of consciousness, substance abuse/dependence or pregnancy.

The drug evaluation studies will include normal subjects and individuals with existing diagnoses of schizophrenia. They will range in age from 18-35 years for all studies except those involving memantine, in which case they will range from 18-45 years. Males and females will be included in future studies. Subjects will be given a complete screening physical exam and will be excluded if showing any evidence of cardiovascular disease (e.g., hypertension, arrhythmia). Control subjects will also be screened for evidence of psychopathology or history of substance abuse using a modified SCID-N interview. If either is evident, the subject will be excluded from the study. All subjects will be informed of the nature of the study by a research assistant who will obtain consent if the subject wishes to participate. All subjects will be mentally competent and capable of giving informed consent.

Table 3. Proposed samples for ongoing / planned studies:

Study	Population	Total Sample	Rate	Status
"ONE-DAY" parametric studies	Normal Controls	up to 50/yr	50/yr	as needed
"WITHIN-SUBJECT" amphetamine/COMT	Normal Controls	120	60/yr	ongoing
"WITHIN-SUBJECT" memantine	Normal Controls	30	30/yr	ongoing
"WITHIN-SUBJECT" memantine	schizophrenia	60	24/yr	planned

The proposed study samples (Table 3) reflect both logistical and power consideration (see above, section "8. j. Statistics.") that differ across the several different studies covered by this application. Testing in the "ONE-DAY" session is designed for parametric "mini-studies", and the proposed sample of "up to 50 subjects" per year will allow us to study up to 5 different sets of stimulus parameters, with n's of 10 subjects per study. To study drug effects on PPI in normal control subjects, our target samples have historically been 20-30 subjects per dose; however, with the addition of COMT subgroup analyses, we currently plan to test 120 subjects in the within-subject amphetamine study, over a 2 year period (n=60/year). To study the effects of memantine on PPI and related measures in schizophrenia patients, we are proposing to study a total of 60 subjects: 30 per dose (10 and 20 mg). As this testing will be conducted over 2 - 3 years, we estimate recruitment needs of approximately 2 subjects per month, which will be easily accommodated by our recruitment capacity at the UCSD Medical Center, based on experience over the past 25 years.

Records and data will be rigorously protected, as described below. Aside from historical and questionnaire data, startle response, negative priming, MCCB, mismatch negativity and gamma band synchronization data will be obtained. Urine will be obtained for toxicological analysis as part of the subject exclusion process. Blood samples will be collected to identify genes that may be associated with PPI or its sensitivity to drugs.

The ethnic population in our male studies from the last 5 years (as we've only studied males exclusively based on drug study exclusion criteria) and is expected in the following years are:

Asian/Pacific Islander	29%
Black (not Hispanic)	3%
Hispanic	10%
White (not Hispanic)	56%
Other/unknown	2%

The ethnic population in our non-drug female studies from the last 5 years and is expected in the following years are:

Asian/Pacific Islander	12.5%
Black (not Hispanic)	2.5%
Hispanic	8.75%
White (not Hispanic)	72.5%
Other/unknown	3.75%

These numbers reflect the location of where we typically recruit subjects.

11. RECRUITMENT

1) Control subjects: Recruitment of clinically normal control subjects will follow our established and successful methods, using public announcements (e.g., newspapers and bulletin boards, online advertisements). Fliers that are posted and faxes that are sent to the UCSD Guardian (on-campus newspaper) are enclosed. Phone screening excludes subjects with a history of serious medical or neurologic illness or trauma, mental illness (including substance abuse), psychotropic medication use, known or suspected pregnancy or hearing problems. Screening is repeated at the time of testing, and a urine sample is collected for toxicological analysis (exclusion for illicit substances). The SCID is used with our published criteria to exclude theoretically "psychosis-prone" control subjects, important for

comparisons with schizophrenia patients. A handedness questionnaire is used to distinguish right and left handed subjects and a questionnaire for evaluating sexual preference is used to identify gender orientation, an important control in studies of sexual dimorphism of sensorimotor gating. Subjects also fill out cognitive and personality questionnaires: the Eysenck Personality Questionnaire (EPQ), Tridimensional Personality Questionnaire (TPQ), the Sensation Seeking Scale - Form V (SSS-V).

2) Schizophrenia patients: Recruitment of schizophrenia subjects will follow our established and successful methods. Patients will be recruited from the UCSD Outpatient Clinic, the UCSD VAMC clinics or community hospitals, and board and care facilities. Clinical assessment of schizophrenia patients follows our established procedures approved by the UCSD IRB for existing protocols (e.g. #071128, [name], PI; #071306, [name], PI). Specifically, after giving informed consent, some schizophrenia patients will be interviewed using the SCID-I/P to ensure that they meet the DSM-IV criteria for schizophrenia. Demographic information, including age, age of onset, duration of illness, number and duration of hospitalizations, socioeconomic status, education, a detailed medication history, medical and psychiatric history, and family history of schizophrenia disorders will be obtained. Positive and negative symptoms of schizophrenia will be assessed during the Schedule for the Assessment of Positive Symptoms (SAPS) and Schedule for the Assessment of Negative Symptoms (SANS). Inclusion criteria include: 1) DSM-IV diagnosis of schizophrenia; 2) Written informed consent to participate in the study; 3) Age \geq 18; 4) Absence of dementia or mental retardation; 5) Urine toxicology negative for recreational drugs; 6) Fluent and literate in English (needed for completion of MCCB). Exclusion criteria include: a) meets DSM-IV criteria for current substance abuse or dependence and has been substance abstinent for less than 30 days; b) a history of traumatic brain injury; c) auditory or visual impairments severe enough to prevent study participation.

Recruitment of female subjects: As per NIH guidelines, it is important to establish whether observed drug effects on these psychophysiological measures are sex-specific. Our current NIMH application thus proposes the use of female subjects in within-subject studies of drug effects on PPI, LI and related measures. At present, approval for studies in females is sought only for studies with amphetamine and memantine. Methods for these studies will be identical to those described above for male subjects, with the following exceptions: 1) urine pregnancy tests ("Surecheck Early Pregnancy Test") will be completed at the time of initial screening and test day 2 (exclusion: positive test); 2) testing will occur only during post-menses days 1-10; 3) blood will be drawn on the morning of testing and stored for possible later hormonal analyses using the GCRC/CTRI laboratory services; a total of 5 cc will be collected by venopuncture using GCRC/CTRI or hospital phlebotomy services.

